3.7.6 Multiplicity Adjustments

A single primary comparison is planned, avoiding any need to adjust p-values for multiple comparisons. The secondary analysis of each dose of mexiletine on the primary pharmacodynamic outcome will be tested at two-tailed $p < 0.027$ following Dunnett's correction for comparing two active treatments to placebo.

3.7.7 Missing Data

The planned mixed model yields estimates that are unbiased conditional on the observed scores under a missing at random assumption. Sensitivity analyses may be pursued to impute missing values or otherwise construct models for unobserved outcomes if more than 20% of participants are missing follow-up data for any reason.

3.8 Safety Analysis

3.8.1 Treatment-emergent Adverse Events

The incidence of TEAEs will be summarized by the number of events of a given classification experienced by participants in each treatment group and by the number and proportion of participants experiencing such an event in each treatment group in the ST sample. TEAEs will be summarized in aggregate across all MedDRA terms and separately by MedDRA system organ class and preferred term.

Aggregate summaries of TEAE grade will include characteristics of: (a) seriousness, (b) severity, (c) relatedness to study drug, (d) relatedness to TMS, (e) relatedness to TTNCS, (f) action taken with study drug, (g) action taken with study procedure, and (h) outcome. For each level of a given TEAE characteristic, summaries will include the number of events of a given classification and by the number and proportion of participants for which that level of a characteristic was the worst they experienced (treating any unknown characteristic as not worst).

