13.7. Analysis of Secondary Efficacy Variable

Equivalent models will be used to analyze other pharmacodynamic markers obtained by TMS and NCS and clinical measures of progression. Frequency of muscle cramping will use a similar generalized linear mixed model assuming that weekly counts follow a negative binomial distribution and including participant-specific random slopes with unstructured covariance of random intercepts and slopes. Pain from cramping and interference from fasciculations will be analyzed in similar models assuming a normal distribution and identity link for pain and a multinomial distribution and cumulative logit link for interference from fasciculations.

Analyses of safety will include frequency of AEs compared by negative binomial regression, proportion of participants experiencing a given AE or SAE classified by MedDRA system organ class or preferred term by Fisher's exact test, occurrence of clinically significant clinical laboratory abnormalities by Fisher's exact, and trends in vital signs and ECG parameters by linear mixed models. Participants will be analyzed according to the treatment actually received. With a plan of 40 participants exposed to mexiletine, the study will have an 80% probability of observing at least one instance of any safety outcome expected to occur in at least 4% of exposed patients, or 8% for events unique to a single dose. Comparisons of event rates across doses will be sensitive only to relatively large differences. The study will have 80% power to detect treatment differences in event rates if the rates in the placebo arm are moderately frequent (20% to 50%) and mexiletine exposure increases the odds at least 6-fold.

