13.8. Selection Criteria

The best dosage level to carry forward in future trials will be based on safety and tolerability as estimated from the rates of AEs, SAEs, mortality, clinical abnormalities, and early termination of study drug or withdrawal from the study. Given the uncertain nature of possible differences in safety and tolerability, absolute criteria cannot be pre-specified.

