3.9.2 Study Drug Compliance and Tolerance

The number of days of exposure to study drug will be summarized by treatment group. Compliance with study drug will be calculated as the number of doses taken divided by the scheduled number of doses taken prior to permanent discontinuation, expressed as a percentage. The proportion of participants judged tolerant of study drug, both those free of intolerance due to an AE and those free of intolerance for any reason, will be summarized by treatment group.

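### SAP 3.8 replaces the between-arm safety comparisons of Protocol 13.7 with by-arm summaries and gives no reason; neither document specifies a tolerability comparison, so the dose choice rests on raw rates

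*SAP*

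**What the plan says.** Protocol 13.7 names four between-arm safety methods:

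- event counts: "Analyses of safety will include frequency of AEs compared by negative binomial regression"
- event proportions: "proportion of participants experiencing a given AE or SAE classified by MedDRA system organ class or preferred term by Fisher's exact test"
- laboratory: "occurrence of clinically significant clinical laboratory abnormalities by Fisher's exact"
- vital signs and ECG: "trends in vital signs and ECG parameters by linear mixed models"

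The same section gives an 80% chance of seeing at least one event of 4% frequency among 40 exposed participants, or of 8% frequency for a single dose. It also states 80% power for event-rate differences when the placebo rate is 20% to 50% and mexiletine raises the odds at least six-fold. It warns that comparisons across doses will detect only fairly large differences.

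SAP 3.8.1 says: "The incidence of TEAEs will be summarized by the number of events of a given classification experienced by participants in each treatment group", together with the number and proportion of participants affected. SAP 3.8.2 to 3.8.4 give means, standard deviations, medians, ranges and proportions by arm for laboratory values, vital signs and weight, and examinations. ECG abnormalities are a safety endpoint in SAP 3.2.3, but 3.8 has no ECG section. Tolerability is handled in SAP 3.2.4 and 3.9.2, where "The proportion of participants judged tolerant of study drug" is summarised by treatment group. The SAP's opening section makes it authoritative over the protocol on matters of analysis.

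Protocol 13.8 states the use to which these data are put: "The best dosage level to carry forward in future trials will be based on safety and tolerability". It adds that absolute criteria cannot be fixed in advance.

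**The concern.** A programmer who follows the SAP will run no safety comparison between arms. The protocol's four methods disappear, and with them the analysis to which its power statement refers. The SAP does not say whether this was intended.

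Safety and tolerability are a secondary objective (SAP 2.2) and the stated basis for choosing the dose to carry forward. No numerical criterion is fixed for that choice, so an estimated difference with its uncertainty is the main safeguard against over-reading chance differences in arms of about 20. The SAP does specify a 600 against 300 mg/day contrast for RMT (3.7.2) and carries it to other continuous endpoints (3.7.3), but not to safety or tolerability. The earlier ALS trial of this drug, shown in Protocol Table 4, reported p-values for each pair of arms, including dose against dose (nausea 8/19 against 1/20, p = 0.008). The present SAP would not produce such a table.

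**Working it through.** **1. Protocol and SAP side by side**

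| Endpoint | Protocol 13.7 | SAP |
|---|---|---|
| AE counts | Negative binomial | Counts by arm (3.8.1) |
| AE and SAE proportions | Fisher's exact | Proportions by arm (3.8.1) |
| Laboratory abnormalities | Fisher's exact | Proportions by arm (3.8.2) |
| Vital signs | Linear mixed model | Descriptive statistics by arm (3.8.3) |
| ECG | Linear mixed model | Endpoint in 3.2.3; no analysis in 3.8 |
| Tolerability | No test named | Proportions by arm (3.2.4, 3.9.2) |

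The first five rows lose a planned comparison. In the last row there was none to lose.

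**2. The protocol's detection probabilities**

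Inputs: 60 participants randomised 1:1:1, so 20 per arm and 40 exposed. The formula is 1 - (1 - p)^n.

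- n = 40, p = 0.04: 1 - 0.96^40 = 0.805
- n = 20, p = 0.08: 1 - 0.92^20 = 0.811

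Both reproduce the stated 80%.

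**3. The protocol's power statement**

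With placebo rate p and odds ratio 6, the mexiletine rate is q = 6p / (1 - p + 6p). For p = 0.20 this is 1.2/2.0 = 0.60. Power is the exact probability, summed over all possible pairs of counts, that the two-sided Fisher p-value is at most 0.05. The documents give no alpha for safety, so 0.05 is an assumption.

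| Placebo rate | Mexiletine rate | Pooled, 40 vs 20 | One dose, 20 vs 20 |
|---|---|---|---|
| 20% | 60.0% | 81.3% | 65.0% |
| 30% | 72.0% | 84.8% | 65.3% |
| 40% | 80.0% | 85.4% | 65.0% |
| 50% | 85.7% | 79.2% | 59.8% |

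The stated 80% reproduces for pooled mexiletine against placebo. For one dose against placebo, 80% power needs an odds ratio of about 8.25 to 11.25, depending on the placebo rate. A normal approximation gives 69% to 78% for 20 against 20 at odds ratio 6, still below 80%. A 600 against 300 mg/day comparison also has 20 per arm.

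**4. What raw rates from 20 per arm can support**

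The counts below are assumed for illustration. Intervals for the risk difference are Newcombe's, built from the two Wilson intervals.

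| Counts | Difference (points) | 95% CI (points) | Fisher p |
|---|---|---|---|
| 4/20 vs 1/20 | 15 | -7 to 37 | 0.34 |
| 6/20 vs 2/20 | 20 | -5 to 43 | 0.24 |
| 6/20 vs 1/20 | 25 | 1 to 47 | 0.09 |

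For the first row, the Wilson limits are 0.081 to 0.416 for 4/20 and 0.009 to 0.236 for 1/20. The lower limit is 0.15 - sqrt((0.20 - 0.081)^2 + (0.236 - 0.05)^2) = -0.07. The upper limit is 0.15 + sqrt((0.416 - 0.20)^2 + (0.05 - 0.009)^2) = 0.37.

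**The case against.** Descriptive safety reporting is a common and defensible choice at this size. Protocol 13.8 bases the dose choice on estimated rates, not on a test, and rates by arm are what the SAP tabulates. The SAP also says that it supplements the protocol, so its silence on tests might leave 13.7 in force.

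The first two points stand in part: the protocol never made the dose choice depend on a significance test. They do not justify leaving out any measure of uncertainty. The third is weaker, because SAP 3.8 sets its own methods for the same endpoints rather than staying silent. At best the two documents are ambiguous.

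Three stronger readings are tempting, and the documents do not support them.

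- **The SAP dropped a planned tolerability comparison.** Protocol 13.7 names no tolerability test, so the comparison was never specified.
- **The SAP withdrew promised confidence intervals.** Protocol 13.7 promises tests and models for safety and mentions no intervals. Their absence is not only the SAP's doing.
- **The 80% power figure is wrong.** Protocol 13.7 speaks of 40 exposed participants and of mexiletine exposure, which most naturally means both doses pooled. On that reading the figure reproduces, and the section already warns about comparisons across doses.

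A practical objection also stands. Many unadjusted comparisons can be over-read, and an interval and a test can appear to disagree: 6/20 against 1/20 has an interval that excludes zero but a Fisher p-value of 0.09.

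**Conclusion.** The concern holds for the discrepancy itself. For adverse events, laboratory abnormalities, vital signs and ECG, the governing SAP replaces the protocol's comparisons with by-arm summaries, or in the case of ECG with nothing, and does not explain why. For tolerability the gap lies in both documents. The result is that a secondary objective and the dose choice in Protocol 13.8 have no between-arm estimate or interval.

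The illustrations show the scale: with 20 per arm, differences of 15 to 20 points can be compatible with no difference. Restoring the tests alone would not give a well-powered choice between doses, since power for 20 against 20 is about 60% to 65% at six-fold odds. That favours estimates with intervals over p-values. The power figures assume a two-sided alpha of 0.05 and full arms of 20, and the example counts are invented. The primary RMT analysis is not affected. The point should be settled before unblinding.

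**What to change.** 1. In SAP 3.8, restore the Protocol 13.7 comparisons for event counts, event proportions, laboratory abnormalities, vital signs and ECG. Otherwise, reconcile the two documents and state why the comparisons were removed. In either case, give ECG its own analysis section.
2. In SAP 3.8.1 and 3.9.2, report risk differences with 95% confidence intervals for any TEAE, any serious TEAE, preferred terms above a stated frequency, and both tolerability proportions. Give these for pooled mexiletine against placebo, each dose against placebo, and 600 against 300 mg/day, because the decision is between doses.
3. Label any p-values for these comparisons as descriptive and unadjusted, and name the interval as the main result so that an apparent conflict with Fisher's test is not over-read.
4. In Protocol 13.7, state that the 80% power at six-fold odds refers to pooled mexiletine against placebo, state the alpha, and note that one dose against placebo has about 60% to 65%.

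The cost is a few sentences and some extra table columns, with no new data. The downside is a larger set of unadjusted comparisons that must be read as descriptive.

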14.1. Definitions of AEs, Suspected Adverse Drug Reactions & SAEs

14.1.1. Adverse Event and Suspected Adverse Drug Reactions

An AE is any unfavorable and unintended sign (including a clinically significant abnormal laboratory finding, for example), symptom, or disease temporally associated with a study, use of a drug product or device whether or not considered related to the drug product or device.

Adverse drug reactions (ADR) are all noxious and unintended responses to a medicinal product related to any dose. The phrase “responses to a medicinal product” means that a causal relationship between a medicinal product and an AE is at least a reasonable possibility, i.e., the relationship cannot be ruled out. Therefore, a subset of AEs can be classified as suspected ADRs, if there is a causal relationship to the medicinal product.

Examples of AEs include: new conditions, worsening of pre-existing conditions, clinically significant abnormal physical examination signs (e.g., skin rash, peripheral edema), or clinically significant abnormal test results (e.g., lab values or vital signs), with the exception of outcome measure results, which are not being recorded as AEs in this trial (they are being collected, but analyzed separately). Stable chronic conditions (e.g., diabetes, arthritis) that are present prior to the start of the study and do not worsen during the trial are NOT considered AEs. Chronic conditions that occur more frequently (for intermittent conditions) or with greater severity, would be considered as worsened and therefore would be recorded as AEs.

AEs are generally detected in two ways:

Clinical → symptoms reported by the subject or signs detected on examination.

Ancillary Tests → abnormalities of vital signs, laboratory tests, and other diagnostic procedures (other than the outcome measures, the results of which are not being captured as AEs).

For the purposes of this study, symptoms of progression/worsening of ALS, including ‘normal’ progression, will be recorded as AEs.

The following measures of disease progression will not be recorded as AEs even if they worsen (they are being recorded and analyzed separately): vital capacity results and ALSFRS-R results.

If discernible at the time of completing the AE log, a specific disease or syndrome rather than individual associated signs and symptoms should be identified by the SI and recorded on the AE

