14.2.1. Assessment of Adverse Events

At each visit (including telephone interviews), the subject will be asked if they have had any problems or symptoms since their last visit in order to determine the occurrence of AEs. If the subject reports an AE, the SI will probe further to determine:

1. Type of event
2. Date of onset and resolution (duration)
3. Severity (mild, moderate, severe)
4. Seriousness (does the event meet the above definition for an SAE)
5. Causality, relation to investigational product and disease
6. Action taken regarding investigational product
7. Outcome

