14.2.2. Relatedness of Adverse Event to Investigational Product

The relationship of the AE to the investigational product should be specified by the SI using the following definitions:

1. Not Related: Concomitant illness, accident or event with no reasonable association with treatment.
2. Unlikely: The reaction has little or no temporal sequence from administration of the investigational product, or a more likely alternative etiology exists.
3. Possibly Related: The reaction follows a reasonably temporal sequence from administration of the investigational product and follows a known response pattern to the suspected investigational product; the

reaction could have been produced by the investigational product or could have been produced by the subject's clinical state or by other modes of therapy administered to the subject. (Suspected ADR)

4. Probably Related: The reaction follows a reasonably temporal sequence from administration of investigational product; is confirmed by discontinuation of the investigational product or by re-challenge; and cannot be reasonably explained by the known characteristics of the subject's clinical state. (Suspected ADR)

5. Definitely Related: The reaction follows a reasonable temporal sequence from administration of investigational product; that follows a known or expected response pattern to the investigational product; and that is confirmed by improvement on stopping or reducing the dosage of the investigational product, and reappearance of the reaction on repeated exposure (Suspected ADR).

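### SAP 3.8.1 ranks an unknown adverse event characteristic below any known level in the participant worst-level tables, so those tables can only err towards a more favourable profile

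*SAP*

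**What the plan says.** SAP 3.8.1 plans three kinds of summary of treatment-emergent adverse events (TEAEs) in the Safety and Tolerability sample.

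1. Incidence, by events and by participants: "TEAEs will be summarized in aggregate across all MedDRA terms and separately by MedDRA system organ class and preferred term". No characteristic of the event is needed to be counted here.
2. Event counts by level: "For each level of a given TEAE characteristic, summaries will include the number of events of a given classification".
3. Participant counts by worst level: the "number and proportion of participants for which that level of a characteristic was the worst they experienced", with the qualification "treating any unknown characteristic as not worst".

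The qualification governs only the third kind. It covers all eight characteristics listed there: seriousness, severity, relatedness to drug, to TMS and to TTNCS, action taken with drug and with procedure, and outcome. SAP 3.2.3 makes the proportion of participants by these characteristics a safety endpoint, with the whole Safety and Tolerability sample as denominator.

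Protocol 14.1.1 defines an adverse drug reaction as a response for which "a causal relationship between a medicinal product and an AE is at least a reasonable possibility, i.e., the relationship cannot be ruled out". Protocol 14.2.2 adds that "The relationship of the AE to the investigational product should be specified by the SI using the following definitions" and gives five levels, from not related to definitely related. Protocol 14.2.1 gives three severity levels. Neither scale has an unknown level, and no levels are listed for outcome.

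**The concern.** On severity and relatedness the protocol offers no unknown category, so an unknown there is an assessment that was not made. For outcome it usually means that the end of the event was not seen. Ranking such an entry below every known level treats it as if it were the most benign value on the scale.

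At stake are the participant-level proportions by severity, relatedness and outcome. Incidence tables show that an event occurred, but not whether it was severe, related or unresolved. Event counts by level cannot be turned into participant proportions, because one participant may contribute several events. The worst-level table is therefore the only planned display of these endpoints at participant level. The SAP plans no alternative tabulation, and its missing-data section (3.7.7) concerns the outcome models and not adverse event fields. It also does not say where a participant whose only value is unknown is placed.

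**Working it through.** **Direction of the error.** Order the levels of a characteristic from best to worst. For one participant, let K be the worst level among events with a known value, and U the true but unrecorded level of the event coded unknown.

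- Displayed worst level under SAP 3.8.1: D = K.
- True worst level: T = max(K, U), so T ≥ D in every case.

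The rule leaves the displayed level correct when U ≤ K and too favourable when U > K. It is never too unfavourable.

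| Participant's events | Shown under SAP 3.8.1 | Possible true worst level |
|---|---|---|
| not related + relatedness unknown | not related | any of the five levels |
| mild + severity unknown | mild | mild, moderate or severe |
| recovered + outcome unknown | recovered | recovered or worse |
| unknown only | not stated | any level |

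**Upper bound per participant.** About 60 participants are randomized 1:1:1 (Protocol 5.1), so 60/3 = 20 per arm. One reclassified participant is 1/20 = 5 percentage points of that arm's proportion; three would be 3/20 = 15 points. The documents give no rate of unknowns, so the counts of one and three are assumptions. The 5 points are reached only if that participant's unknown event truly was at the worse level and no other event of theirs was already recorded at that level or worse.

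**The plan's own safety figure.** Protocol 13.7 states an 80% chance of seeing at least one event with a rate of 4% among 40 exposed, or 8% for a single dose (20 exposed). The formula is 1 − (1 − p)^n.

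- 1 − 0.96^40 = 0.805
- 1 − 0.92^20 = 0.811

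Both reproduce the stated 80%. The figure concerns any occurrence of an event, so the worst-level rule does not change it.

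For illustration only, suppose a share u of such events is coded unknown and shown at a lower level. The chance that at least one appears at its true level in the worst-level table is 1 − (1 − p(1 − u))^n.

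| u (assumed) | p = 4%, n = 40 | p = 8%, n = 20 |
|---|---|---|
| 0 | 80.5% | 81.1% |
| 10% | 76.9% | 77.6% |
| 20% | 72.8% | 73.4% |

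The same events still appear in the incidence tables.

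**Protocol against SAP on relatedness.** The wording in Protocol 14.1.1, "is at least a reasonable possibility, i.e., the relationship cannot be ruled out", belongs to a definition of a drug reaction. An event whose relationship was never assessed has not had that relationship ruled out, yet the SAP places it below events judged not related. That is a tension. It is not a contradiction, because the protocol text does not say how a missing assessment is to be tabulated.

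**The case against.** The case for leaving the rule alone has several sound parts.

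- A reader might infer that the rule hides events from the safety tables. It does not: incidence overall and by MedDRA term, and event counts by level, include every TEAE.
- A reader might infer that the SAP breaches the protocol. It does not. The definition in Protocol 14.1.1 bears at most on drug relatedness, one of eight characteristics, and says nothing on severity or outcome. Protocol 14.2.2 labels only its possible, probable and definite levels as suspected reactions. The SAP also declares itself authoritative on analysis matters.
- A reader might infer that dose selection is distorted. Protocol 13.8 names rates of adverse events and serious adverse events, mortality, clinical abnormalities, and early termination or withdrawal. Worst-level tables are not among these inputs, and tolerability in SAP 3.2.4 does not use them.
- A reader might expect unknowns to gather in early leavers at the higher dose. Monitoring does end at consent withdrawal or loss to follow-up (Protocol 14.1.1), so unknown outcomes are possible there. But participants who stop drug are encouraged to stay on study (5.6), events are to be followed after stopping drug (6.4), relationship, severity and outcome are required log entries (14.2.3), and the database locks only after queries are resolved (15.1.3). The documents give no unknown rate by arm.
- Coding every unknown as the worst level assigns grades that nobody made and can overstate harm by the same 5 points per participant.

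The first four points limit the scope of the concern and stand. The last is a good reason not to recode severity in the main table. None of them answers the one-directional ranking, or the silence on participants with only unknown values. That the rule is prespecified and identical across arms does not make the proportions unbiased.

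**Conclusion.** The point holds in a narrow form. In the participant worst-level summaries, and only there, SAP 3.8.1 uses a rule whose error can run only towards a more favourable profile, in proportions listed as safety endpoints. For drug relatedness it sits in tension with the protocol's definition of a drug reaction, without contradicting it.

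The size cannot be estimated. The bound is 5 percentage points per affected participant in an arm of 20. A figure of 5 to 15 points should not be read as the expected understatement, since it assumes one to three affected participants and a truly worse level for each. If data cleaning leaves no unknowns, the effect is nil.

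The conclusion rests on reading the rule as placing unknown below every known level, which is its natural sense. It is a low-cost improvement to descriptive safety reporting, with no bearing on the primary analysis or the sample size.

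**What to change.** Amend SAP 3.8.1 for the worst-level tables as follows.

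- **Relatedness to study drug:** count unknown as related. One way is to rank it above unlikely and below possibly related, and include it in the related subtotal.
- **Outcome:** rank unknown above recovered and below not recovered, and list the outcome levels in order.
- **Every characteristic:** show unknown as its own row, and state that participants whose only value is unknown are counted there.
- **Severity:** keep the main table on recorded grades with the unknown row, and add a sensitivity table with unknown counted as severe.

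The cost is a few sentences, one row per table and one sensitivity table. Some proportions will look slightly less favourable, and the related proportion may be somewhat overstated; the unknown row lets the reader see by how much at most.
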